5.3 Procedures

All parents of participating children will be offered the opportunity to participate in the study and will be asked to sign an informed consent form during a routine visit of their child. After verifying eligibility criteria and obtaining informed consent, parents will be randomly assigned via a centralized web-based randomization process to either participate in the BEM group activity or to the control group. If both parents are eligible, they will be allocated to the same study arm.

Once consent to participate has been obtained, parents will receive login credentials for the study's web platform, through which they will be able to complete the required questionnaires. Socio-demographic information of the parents and clinical data related to the child/adolescent will also be collected at enrollment.

Parents will then be invited to participate in either the BEM group activity or the standard activity. At 3 and 6 months after the group activity, parents will be asked to complete the questionnaires again via access to the portal. The glycemic data of the children/adolescents will be derived from continuous glucose monitoring (CGM) measurements and extracted from the electronic medical records provided by the participating diabetes centers.

5.4 Questionnaires

All participants will be asked to complete the following questionnaires on a web platform, both at enrollment and at three and six months after the completion of group activities.

Parenting Stress Index Short form (PSI-SF)

The Parenting Stress Index is designed for the early identification of characteristics that, at the level of parents or the family as a whole, may compromise the normal development and functioning of the child. It aims to identify children with emotional and behavioral disorders as well as parents who may experience their parental role in a dysfunctional manner. The instrument is based on the premise that the stress

experienced by a parent result from a combination of specific characteristics of the child, the parent themselves, and a series of situational factors closely related to the parental role. The Italian validation pertains only to the short form of the test (PSI-SF), which is directly derived from the extended version. The short form is highly practical, easy to administer and interpret, making it particularly useful in clinical settings [14]. The PSI-SF investigates three main domains of stress-related factors, which are attributable to the child's characteristics, the parent's traits, and situational-demographic events. The short form consists of 36 items divided into three subscales: 1) Parental Distress (12 items), which assesses the level of distress a parent is experiencing in their parental role, understood as stemming from personal factors directly related to that role; 2) Dysfunctional Parent-Child Interaction (12 items), focusing on the parent's perception that the child does not meet their expectations and that interactions with the child do not reinforce their parental role; 3) Difficult Child (12 items), centered on key characteristics of the child that make them easy or difficult to manage, often originating from temperament, including behavioral patterns of defiance, disobedience, and demanding behaviors. Additionally, it is possible to calculate a response style score, which evaluates the extent to which the respondent answers the questionnaire with a tendency to present a more favorable image of themselves, thereby minimizing indications of problems or stress in the parent-child relationship.

Patient Health Questionnaire (PHQ9)

The PHQ-9 is a 9-item questionnaire developed as a depression screening tool for use in primary care settings [15]. Each of the nine items corresponds to one of the symptoms listed in Criterion A of the DSM-IV for Major Depressive Disorder [16]. Participants are asked how often they have been bothered by each depressive symptom over the past two weeks. Response options include "not at all," "several days," "more than half the days," and "nearly every day," with corresponding scores of 0, 1, 2, and 3. The PHQ-9 scores range from 0 to 27, with cut-off points of ≥ 5 , ≥ 10 , and ≥ 15 indicating mild, moderate, and severe levels of depression severity, respectively [17]. The psychometric properties of the PHQ-9 are well established [18]. An Italian version of the questionnaire is available.

General Anxiety Disorder (GAD-7)

The GAD-7 is a self-reported questionnaire assessing generalized anxiety, consisting of seven items. The instrument is designed to evaluate the individual's mental health status over the previous two weeks [19]. The items investigate the extent to which the individual has been bothered by feeling nervous, anxious, or on edge; being unable to stop or control worrying; worrying too much about different things; having trouble relaxing; being so restless that it is hard to sit still; becoming easily annoyed or irritable; and feeling afraid as if something awful might happen. Responses are scored 0, 1, 2, or 3 for experiencing these symptoms "not at all," "several days," "more than half the days," and "nearly every day," respectively. The scores are then summed to yield a total ranging from 0 to 21. Cut-off scores of 5, 10, and 15 represent thresholds for mild, moderate, and severe anxiety, respectively. When screening for an anxiety disorder, a recommended threshold for referral for further evaluation is a score of 10 or greater.

The questionnaire has been validated for use both as a screening tool and as a measure of symptom severity [19,20], including in primary care settings [21] and the general population [22]. An Italian version of the questionnaire is available.

Brief Pittsburgh Sleep Quality Index (B-PSQI)

The B-PSQI is the brief version (13 items) of the Pittsburgh Sleep Quality Index (PSQI) [23]. This questionnaire assesses the presence of sleep-related problems over the past month across five domains: sleep duration and efficiency, sleep latency, sleep disturbances, nighttime awakenings, and daytime dysfunction. Each domain is scored on a scale from 0 (best outcome) to 3 (worst outcome). A global score is then calculated by

summing the scores of the individual domains, resulting in a total score ranging from 0 to 15. A total score greater than 4 is indicative of poor sleep quality. An Italian version of the PSQI is available, of which the B-PSQI includes a subset of the original items.

Parental Self-Efficacy for the Management of Diabetes Mellitus (PSESDM)

The PSESDM was developed to assess parental self-efficacy in performing diabetes-related tasks for their young children [24]. This questionnaire, designed for parents of children with diabetes, consists of eight items, each rated on a 5-point Likert scale. Responses range from 1 = "Strongly disagree" to 5 = "Strongly agree." Items 1, 2, 6, and 7 are reverse-scored. The total score ranges from 8 to 40, with higher scores indicating greater parental confidence in managing their child's diabetes.

The Italian version of the instrument will be validated using data from the present study.

Coping Orientation to Problems Experienced (COPE)

The COPE inventory will be used to assess parental adjustment and the adoption of different coping styles. The study will utilize the new Italian version of the instrument (COPE-NVI) [25]. The questionnaire consists of 60 items covering five domains: social support (12 items), avoidance strategies (16 items), positive attitude (12 items), problem-focused coping (12 items), and transcendence orientation (8 items). Participants are asked to indicate how frequently they engage in a given coping strategy when faced with difficult or stressful situations. Responses are rated on a 4-point scale ranging from 1 (I usually don't do this at all) to 4 (I do this a lot). Scores for individual items are summed separately for each of the five domains.

It should be noted that the instruments used in this study are intended for epidemiological and screening purposes and are not to be considered diagnostic tools. Furthermore, the questionnaires are anonymous, as they are completed directly through a dedicated online platform accessed via personal login credentials. Therefore, the researchers will not have access to individual scores. However, if pathological scores are identified, the participant will be informed and, if necessary, referred to specialized services.

6 EVALUATION OF EFFICACY

6.1 Efficacy parameters

The effectiveness of the BEM method compared to a standard educational approach will be assessed by comparing the differences in scores from baseline between the two groups, based on self-administered questionnaires (PSI-SF, PHQ-9, GAD-7, B-PSQI, PSESDM, COPE). Additionally, differences in glycemic indices in children/adolescents (variability, TIR, TAR, TBR) and HbA1c values relative to baseline will be evaluated. The definitions of the glycemic indices and the recommended targets are provided in the table below [26].

Glucose Index	Blood glucose range	Recommended target (% of readings and daily duration)
Variability	Coefficient of variation (%)	≤36%
Time in Range (TIR)	70-180 mg/dl	>70%; >16 hours and 48 min
Time below range (TBR) livello 1	<70 mg/dl	<4%; <1 hour

Time below range (TBR) livello 2	<54 mg/dl	<1%; <15 min
Time above range (TAR) livello 1	>180 mg/dl	<25%; <6 hours
Time below range (TAR) livello 2	>250 mg/dl	<5%; <1 hour

6.2 Frequency of endpoint assessment

Study questionnaires will be completed at baseline (randomization) and at 3 and 6 months following participation in group activities. The primary endpoint will be the comparison between study arms of the difference in PSI-SF questionnaire scores at 3 months post-participation relative to baseline. Clinical parameters (glycemic indices) will be recorded with the same frequency (baseline, 3 and 6 months), and the values considered will be those from the two weeks preceding baseline and follow-up at 3 and 6 months.

7 STATISTICAL CONSIDERATIONS

7.1 Sample Size Calculation

The primary endpoint is the PSI-SF questionnaire score at 3 months after the completion of group activities. The primary efficacy assessment will therefore involve comparing the differences in PSI-SF scores at 3 months relative to baseline between the study arms.

The difference between the two groups in changes of PSI-SF scores will be expressed in terms of effect size (the difference in scores between the two groups divided by the common standard deviation at baseline). It is widely accepted in the literature that an effect size of at least 0.5 can be considered clinically relevant [27]. From the previous study [13], baseline PSI-SF values were 75.4 ± 2.5 ; therefore, an effect size of 0.5 would correspond to a difference of 1.25 between groups.

To detect an effect size of at least 0.5 with a statistical power of 80% ($\alpha=0.05$), at least 64 parents per group need to be evaluated. Assuming a dropout rate of 15%, a total of 150 parents will be enrolled (75 per group)

7.2 Statistical Analysis

All subjects enrolled in the study will be included in the analysis.

Descriptive data will be expressed as means and standard deviations or as medians and interquartile ranges for continuous variables, and as percentages for categorical variables.

Group comparisons for descriptive variables will be performed using Student's t-test or the Mann-Whitney U test for continuous variables, and the chi-square test for categorical variables.

Regarding the primary endpoint (difference in PSI-SF scores at 3 months compared to baseline), the comparison between study arms will be conducted using mixed-effects models for repeated measures (MMRM), which will include the baseline outcome value as a linear covariate and the study arm as a fixed effect. MMRM accounts for within- and between-subject correlations through a variance-covariance matrix with an autoregressive order 1 structure.

Similarly, comparisons between study arms for secondary endpoints related to questionnaire scores and glucometric measures (differences at 3 and 6 months compared to baseline) will be performed using MMRM.

These models will include the baseline value of the respective outcomes as a linear covariate and the study arm as a fixed effect. Results will be expressed as estimated means with 95% confidence intervals.

In addition to the analysis of the entire sample, subgroup analyses will be conducted separately based on parent sex and children/adolescents' age (<10 years and ≥ 10 years).

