2.2.2 Secondary

- Difference in PSI-SF (Parental Stress Index Short-Form) scores after 6 months of participation in the group activities compared to baseline;
- Difference in the scores of the individual components of the PSI-SF questionnaire (Parental Distress, Parent-Child Dysfunctional Interaction, Difficult Child) after 3 and 6 months of participation in the group activities compared to baseline;
- Difference in the scores of the Patient Health Questionnaire (PHQ-9) for the assessment of depression and depressive symptoms after 3 and 6 months of participation in the group activities compared to baseline;
- Difference in the scores of the General Anxiety Disorder (GAD-7) questionnaire for the assessment of anxiety and anxious symptoms after 3 and 6 months of participation in the group activities

compared to baseline;

- Difference in the scores of the Brief Pittsburgh Sleep Quality Index (B-PSQI) for the assessment of sleep disturbances after 3 and 6 months of participation in the group activities compared to baseline;
- Difference in the scores of the Parental Self-Efficacy for the Management of Diabetes Mellitus (PSESDM) questionnaire for the evaluation of self-efficacy perception in managing their child's diabetes after 3 and 6 months of participation in the group activities compared to baseline;
- Difference in the scores of the Coping Orientation to the Problems Experienced - Italian Version (COPE-NVI) questionnaire for assessing parental adaptation and coping strategies after 3 and 6 months of participation in the group activities compared to baseline;
- Difference in glucometric data of children/adolescents (variability, Time In Range [TIR], Time Above Range [TAR], Time Below Range [TBR], HbA1c) after 3 and 6 months of participation in the group activities compared to baseline;
- Additionally, a qualitative analysis will be conducted to further explore parents' experiences regarding their perception of their child (e.g., "How do I see my child's life now?").

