4.3 Procedures for assigning interventions in the study

4.3.1 Randomization procedure

After verification of the eligibility criteria, the parents will be assigned via centralized web-based randomization to participate in either the BEM group activity or the control group (1:1 randomization). In cases where both parents are eligible, they will be allocated to the same study arm. The randomization will be stratified by center.

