11 DATA COLLECTION

The medical history and data of children with T1D, who are the offspring of study participants, will be extracted from their medical records and recorded on a pseudonymized eCRF. At study entry, the following information regarding the child will be collected: sex, age, level of education, ethnicity, body weight, height, duration of diabetes, diabetes treatment, presence of diabetes-related complications, last HbA1c value, glucometric data from continuous glucose monitoring (TIR, TAR, TBR), presence of other chronic conditions, hospitalizations in the past year due to severe hypoglycemia, diabetic ketoacidosis, or other reasons, participation in school camps, and engagement in physical activity. The medical records will serve as source documents for these data.

The data required by the protocol will be entered into an electronic case report form (eCRF). The quality and completeness of the data will be verified during and after data collection.

Regarding the parents, the collected data will include age, education level, employment status, marital status (married or cohabiting, separated, divorced, widowed, single/celibate), number of children, household size, and presence of other family members with diabetes. These details will be directly recorded by the parents through personalized access to the dedicated web platform used for the study, which will also facilitate questionnaire completion.

Throughout and at the end of the study, a database review will be performed to monitor data quality and completeness. Any modifications will be tracked using audit trail systems. Once all queries are resolved, the database will be frozen. The database will then be archived and subjected to backup and storage policies in accordance with GCP guidelines, and made available for subsequent audits if required. Raw data will be stored in a database for statistical analysis, which will be conducted after database lock. The impact of missing data on the primary endpoint will be assessed, and the need for imputation techniques will be considered.

An anonymized database will be managed and analyzed at the Center for Outcomes Research and Clinical Epidemiology (CORESEARCH s.r.l.) in Pescara.

12 Publication Policy

All analysis results will be produced solely and exclusively in aggregated form and in a manner that is not attributable, either directly or indirectly, to any individual patient.

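### Section 7.2 does not make the child the unit of analysis for the glycaemic endpoints; read literally, a child with both parents enrolled counts twice and standard errors are too small

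*Protocol*

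**What the plan says.** The recruited and counted unit is the parent. Protocol section 7.1 plans for "a total of 150 parents will be enrolled (75 per group". Couples are allowed and are kept together; section 4.3.1 states: "In cases where both parents are eligible, they will be allocated to the same study arm".

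Section 7.2 opens its analysis rules with "All subjects enrolled in the study will be included in the analysis". It describes an MMRM for the PSI-SF with the baseline value and study arm as terms and an AR(1) covariance structure. It extends this model to "comparisons between study arms for secondary endpoints related to questionnaire scores and glucometric measures", again with only baseline and arm named. Subgroups by parent sex and by child age follow and are not limited to any class of outcome.

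The glycaemic endpoints are measured on the child. Section 2.2.2 lists "Difference in glucometric data of children/adolescents (variability, Time In Range [TIR], Time Above Range [TAR], Time Below Range [TBR], HbA1c". Section 5.3 gives the source: "The glycemic data of the children/adolescents will be derived from continuous glucose monitoring (CGM) measurements". Section 11 says that data on the children, "who are the offspring of study participants, will be extracted from their medical records and recorded on a pseudonymized eCRF". It does not say whether the eCRF holds one record per child or one per enrolled parent. On timing, section 6.2 says "the values considered will be those from the two weeks preceding baseline and follow-up at 3 and 6 months".

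**The concern.** For a questionnaire, two parents of one child give two real measurements, which may be correlated. For TIR, TAR, TBR, glucose variability and HbA1c there is one child and one source of data. If the analysis set is built from enrolled parents, that child's values appear on two rows, both in the same arm, and the model treats them as two independent subjects.

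The stated covariance structure does not repair this. Section 7.2 says the model handles correlation within and between subjects, but AR(1) describes how correlation decays across the visits of one subject. It does not link two parents' rows that hold the same child's data.

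Three things follow. Confidence intervals for the glycaemic endpoints would be too narrow. The type I error for these comparisons would exceed its nominal level. Children with two participating parents would get double weight. In addition, a parent-sex subgroup applied to glycaemic outcomes would place the same child's data in both the mothers' and the fathers' subgroup.

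**Working it through.** **The plan's own figure.** Section 7.1 uses an effect size of 0.5, 80% power and α = 0.05. Sidedness is not stated; two-sided reproduces the result. The noncentral t distribution gives power 0.7952 at 63 per group and 0.8015 at 64, so 64 per group is right. For 15% dropout, 128/0.85 = 150.6, in line with the stated 150. This calculation is for the PSI-SF; the protocol gives no sample size, power or error rate for the glycaemic endpoints.

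**Inputs for the check.**
- Rows: N = 150 parents, 75 per arm (section 7.1).
- Couples share an arm (section 4.3.1).
- p = share of enrolled parents whose co-parent is also enrolled. Not in the protocol, so taken over the range 0 to 1.
- Assumption: the two rows of a couple are exact copies (correlation 1).

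**Design effect.** There are Np/2 children on two rows and N(1 − p) children on one row. With m_i rows for child i:

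Σm_i²/N = [4 × Np/2 + N(1 − p)]/N = 1 + p.

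The standard error from a model that ignores the duplication is 1/√(1 + p) of the true one. The true rejection rate of a nominal 5% test is 2 × [1 − Φ(1.96/√(1 + p))]. The number of distinct children is 150 × (1 − p/2).

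| p | 1 + p | Reported SE / true SE | True type I error | Multiple of 5% | Children among 150 parents |
|---|---|---|---|---|---|
| 0 | 1.00 | 1.00 | 5.0% | 1.0 | 150 |
| 25% | 1.25 | 0.89 | 8.0% | 1.6 | 131 |
| 50% | 1.50 | 0.82 | 11.0% | 2.2 | 112 or 113 |
| 75% | 1.75 | 0.76 | 13.8% | 2.8 | 94 |
| 100% | 2.00 | 0.71 | 16.6% | 3.3 | 75 |

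Setting the rejection rate to 15% and solving for p gives p ≈ 0.85, so threefold inflation needs about 85% of parents to be enrolled as couples.

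**Simulation.** Change from baseline at one follow-up visit was analysed by ANCOVA with 75 parent rows per arm, 6,000 runs per scenario and no true effect. This is a simplification of the two-visit MMRM. Rejection rates on parent rows were 0.047, 0.075, 0.104, 0.142 and 0.172 for p = 0, 25%, 50%, 75% and about 99%. With each child used once, they lay between 0.047 and 0.055 in every scenario.

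**If the copies are not exact.** With correlation ρ between a couple's two rows, the design effect becomes 1 + pρ. The table can then be read at pρ in place of p.

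**The case against.** The strongest objection is that the protocol never says glycaemic data are analysed per parent. The sentence on including all enrolled subjects reads as a definition of the analysis population and mentions neither glycaemic data nor the unit. Sections 2.2.2 and 5.3 attribute these data to the children. Section 11 keeps the children's eCRF data apart from what parents enter on the web platform. One record per child fits this text, and an SAP that is not shown may specify it. This stands in part: double counting is the literal consequence of section 7.2, not a stated intention. But section 7.2 is not silent. It fixes the population, the model and its terms, and for a child-level outcome in a trial that enrols couples these lead to double counting unless a rule is added. Parent-sex subgroups without limit to parent-reported outcomes point the same way.

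Other parts of the objection hold and limit the point:
- A reader might infer that false positives are tripled. The protocol gives no couple rate, so this is not supported as an expectation; with no couples there is no inflation.
- Exact duplication assumes that both parents share baseline and follow-up dates. Section 4.3.1 puts them in the same arm, but nothing says they attend the same session. Different dates would give different two-week CGM windows under section 6.2, and a correlation below 1.
- A reader might conclude that the duplicates must be deleted. That is not the only valid remedy: standard errors clustered by child or family also give valid inference, and the double weight is then a choice of estimand.
- The objective in section 2.1 concerns stress and well-being in parents. The glycaemic measures are one item in a long secondary list.

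**Conclusion.** The point holds as a flaw in what section 7.2 fixes: it carries a parent-level analysis over to child-level outcomes without making the child the unit or adding a child or family term. If the section is followed literally and the rows are exact copies, the reported standard error is 89% to 71% of the true one, and the type I error is 8.0% to 16.6%, as p runs from 25% to 100%. The lower part of the range applies if few couples enrol or if their dates differ.

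The documents do not support saying that the sponsor plans to count children twice, nor that any particular inflation will occur. The PSI-SF primary endpoint and its sample size are not touched by this point, because the PSI-SF is measured on each parent. The change should be made because it is cheap and alters the intervals that would be reported for the children, but it concerns secondary endpoints only.

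**What to change.** Add to section 7.2, and carry into the SAP, that glycaemic endpoints are analysed with one record per child per visit, in the family's randomised arm, whether one or both parents take part. If parent rows are kept instead, require standard errors clustered by child or family and state that children with two participating parents carry double weight. If a couple's dates can differ, say which parent's dates define the child's CGM windows.

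Hold a child/family ID in the analysis data set. Section 11 describes an anonymised analysis database and mentions no such key, so it should be secured before database lock. Report the number of children beside the number of parents for each glycaemic result. Restrict the parent-sex subgroup to parent-reported outcomes; the child-age subgroup can stay for both.

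The cost is a few sentences and one identifier. The downside is a smaller n for the glycaemic endpoints (between 75 and 150 children among 150 parents, before any loss to follow-up, if each child has at most two enrolled parents and each parent contributes one child) and correspondingly wider confidence intervals.

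### The MMRM in section 7.2 lists only baseline and study arm, so a literal fit to both visits estimates a 3- and 6-month average, not the 3-month primary effect

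*Protocol*

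**What the plan says.** The target is stated consistently. Section 6.2: "The primary endpoint will be the comparison between study arms of the difference in PSI-SF questionnaire scores at 3 months post-participation relative to baseline". Section 7.1 describes the primary assessment as "comparing the differences in PSI-SF scores at 3 months relative to baseline between the study arms". Section 7.2 opens the analysis with "Regarding the primary endpoint (difference in PSI-SF scores at 3 months compared to baseline), the comparison between study arms will be conducted using" an MMRM. PSI-SF at 6 months is a separate secondary endpoint (section 2.2.2 and the synopsis, Study endpoint).

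For the primary model, section 7.2 gives the fixed terms as "which will include the baseline outcome value as a linear covariate and the study arm as a fixed effect" and the covariance as follows: "MMRM accounts for within- and between-subject correlations through a variance-covariance matrix with an autoregressive order 1 structure". For the secondary endpoints it promises comparisons ("differences at 3 and 6 months compared to baseline) will be performed using MMRM") and repeats the same two terms: "These models will include the baseline value of the respective outcomes as a linear covariate and the study arm as a fixed effect". On reporting: "Results will be expressed as estimated means with 95% confidence intervals". The synopsis (Statistical aspects) gives the same two terms and the same covariance. Nowhere does the protocol name a visit effect, an arm-by-visit interaction or a 3-month contrast.

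**The concern.** Baseline enters as a covariate, so the only repeated outcomes are the 3- and 6-month scores. The AR(1) matrix does something only if both are in the model. With both in and only baseline and arm as fixed terms, there is one arm coefficient for two visits. One coefficient cannot supply both the 3-month primary and the separate 6-month secondary.

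If the model is instead fitted one visit at a time, the target is right but the repeated-measures and AR(1) wording has no function. The text does not say which fit is meant.

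An analyst who follows the listed terms on both visits would report an average over 3 and 6 months as the 3-month result. If the effect of a three-day programme fades, the 3-month effect is understated and power falls. If the effect appears only late, a 3-month benefit could be claimed where none exists.

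**Working it through.** **The plan's own sample size.** For a difference of 1.25, SD 2.5, two-sided α = 0.05 and 80% power (section 7.1; two-sidedness is assumed), the two-sample t-test needs 64 per group (power 0.801). This agrees with the protocol and is not in dispute.

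**What the listed model estimates.** Let d3 and d6 be the true arm differences at 3 and 6 months, v the residual variance at each visit after baseline adjustment, and c the residual covariance between visits. With two visits and equal variances, generalised least squares gives each visit of a completer the same weight, 1/(v + c). The arm coefficient is therefore (d3 + d6)/2. Adding a visit main effect without the interaction leaves it at (d3 + d6)/2; only the arm-by-visit term separates the two differences.

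**Assumed inputs.** The protocol gives no correlations and no 6-month effect. Assumed, in SD units: baseline to follow-up rb = 0.6 (range 0.5 to 0.7) and 3 to 6 months r36 = 0.7 (range 0.6 to 0.8), with 64 per arm, complete data, and clustering by couple or camp ignored. One SD is 2.5 points, so 0.50 SD is 1.25 points.

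- v = 1 − 0.6² = 0.64; c = 0.7 − 0.6² = 0.34; variance of the two-visit mean = (0.64 + 0.34)/2 = 0.49
- SE of the arm-only coefficient = √(2 × 0.49/64) = 0.124
- SE of the 3-month contrast = √(2 × 0.64/64) = 0.141
- Power = Φ(effect/SE − 1.96)
- Coverage of the true 3-month difference = Φ(1.96 − b/SE) − Φ(−1.96 − b/SE), where b = d3 − (d3 + d6)/2

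| d3, d6 (SD) | Arm-only estimate | Power, arm-only | Power, 3-month contrast | Coverage of d3, arm-only |
|---|---|---|---|---|
| 0.50, 0.25 | 0.375 SD (0.94 points) | 86% (75–97%) | 94% (90–98%) | 83% (75–86%) |
| 0.50, 0 | 0.25 SD (0.63 points) | 52% (42–72%) | 94% (90–98%) | 48% (28–58%) |
| 0.50, 0.50 | 0.50 SD (1.25 points) | 98% | 94% | 95% |

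Ranges are over all nine pairs of correlations. In the reverse case (d3 = 0, d6 = 0.50) the arm-only coefficient is again 0.25 SD, so it rejects in 52% (42–72%) of trials although there is no 3-month difference.

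**Without any gain from baseline adjustment.** With SD 2.5 and a between-visit correlation of 0.3 to 0.7, the 3-month contrast has 81% power. The arm-only test has 63–75% if the effect halves and 34–42% if it vanishes. In the reverse case it rejects in 34–42% of trials.

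**Missing 6-month scores.** With a fraction m missing at random, the weight on 3 months is proportional to (1 − m)/(v + c) + m/v and that on 6 months to (1 − m)/(v + c). Taking m = 0.15 (the protocol's dropout figure; its timing is assumed): 0.85/0.98 + 0.15/0.64 = 1.102 against 0.867, so the 3-month weight is 1.102/1.969 = 0.56 (range 0.55 to 0.57). The two fading scenarios are then reported as 0.39 and 0.28 SD (0.97 and 0.70 points). What is estimated therefore also depends on dropout.

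**Simulation check.** 3,000 trials per scenario, two-visit AR(1) fitted by REML. With complete data, baseline plus arm gave 0.377, 0.250 and 0.501 SD in the order of the table, with rejection 86%, 52% and 98% and coverage 84%, 49% and 94%. With visit and arm-by-visit added, the 3-month contrast gave 0.502, 0.498 and 0.500 SD, with rejection 95%, 94% and 93% and coverage 95%, 95% and 94%.

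**The case against.** The strongest reply is that the list of terms need not be exhaustive. Stating that a model will include two terms does not exclude others, an MMRM conventionally carries visit and arm-by-visit effects, and a full list of fixed effects is normally SAP content. Section 7.2 also ties the primary to 3 months and promises differences at 3 and 6 months, which a pooled coefficient cannot deliver. Read as a whole, it points to visit-specific estimates.

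This stands in part: the mis-targeting is conditional, and the analysis will not necessarily be wrong. But the protocol did not leave the model to the SAP. It stated the fixed terms and the covariance, gave the same list in section 7.2 (twice) and in the synopsis, and each time left out the term that defines the endpoint. A SAP that followed the list would carry the error forward; one that departed from it would have to depart from the protocol.

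It is also fair that the power and coverage figures rest on assumed inputs and move a good deal with them. Nothing in the protocol says the effect will vanish by 6 months, and with a sustained effect the pooled test is unbiased and slightly more powerful. The figures are illustrations. The algebraic mismatch needs none of them.

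**Conclusion.** The concern holds. As written, the model does not target the stated 3-month endpoint unless the arm difference is the same at 3 and 6 months. With complete data and equal variances, a literal fit to both visits returns (d3 + d6)/2. Under the central assumptions, an effect that halves by 6 months is understated by a quarter (0.375 instead of 0.50 SD), and one that disappears by 6 months is understated by half. The size depends on the unknown 6-month effect, the correlations and the pattern of dropout. It should be fixed, because it concerns the primary result and is cheap to correct. Confidence is medium, since the wording allows a fuller model.

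**What to change.** In section 7.2 and the synopsis, add categorical visit and arm-by-visit as fixed effects. Name the arm difference at the 3-month visit as the primary test and the arm difference at 6 months as the secondary. Use the same model for the other questionnaire scores and the glycaemic measures.

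The cost is a change of wording and two extra model parameters, with no new data and no change in sample size. If the effect is sustained, the 3-month contrast has slightly less power than the pooled test (about 94% against 98% under the central assumptions).
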